## LIST OF ABBREVIATIONS

ABBREVIATION	DEFINITION
6MWT	Six-Minute Walk Test
AE	adverse event
BMI	body mass index
CEC	Clinical Events Committee
CI	confidence interval
CK-MB	creatine phosphokinase MB isoenzyme
CSR	Clinical Study Report
DMD	Duchenne muscular dystrophy
DSMB	Data Safety Monitoring Board
DSA	donor specific antibodies
ECG	electrocardiogram
ELISPOT	enzyme-linked immunosorbent spot
EOS	end of study
FBS	fetal bovine serum
FEF 25-75%	forced expiratory flow at 25-75% of FVC
FET	forced expiratory time
FEV 1	forced expiratory volume in 1 second
FVC	forced vital capacity
HbA1c	glycosylated hemoglobin
HBsAg	hepatitis B surface antigen
HCV	hepatitis C virus
HIV	human immunodeficiency virus
HLA	human leukocyte antigen
ICH	International Conference on Harmonisation
IL-10	Interleukin 10
IP	investigational product
ITT	intent-to-treat
LGE	late gadolinium enhancement
LS	least-squares
LTfUP	Long-Term Follow-up
LV	left ventricular
LVEDV	LV end diastolic volume
LVEF	left ventricular ejection fraction
LVESV	LV end systolic volume
M	million
MACE	major adverse cardiac event
MAR	missing at random

---

MedDRA	Medical Dictionary for Regulatory Activities
MFI	mean fluorescence intensity
MI	myocardial infarction
mITT	modified intent-to-treat
ML	maximum likelihood
MNAR	missing not at random
MRA	mineralocorticoid receptor antagonist
MRI	magnetic resonance imaging
PedsQL	Pediatric Quality of Life
PEF	peak expiratory flow
PHA	phytohemagglutinin
PODCI	Pediatric Outcomes Data Collection Instrument
PT	Preferred Term
PUL	Performance of Upper Limb
QoL	quality of life
SAE	serious adverse event
SAP	Statistical Analysis Plan
SD	standard deviation
SDF1	stromal cell derived factor 1
SOC	System Organ Class
TEAE	treatment-emergent adverse event
TFLs	tables, figures, and listings
TMPG	TIMI myocardial perfusion grade
VT	ventricular tachycardia
WHO-DD	World Health Organization Drug Dictionary

## PREFACE

The purpose of this statistical analysis plan (SAP) is to describe the planned statistical analyses and reporting for Capricor Protocol CAP-1002-DMD-01 (HOPE). The planned analyses identified in this SAP may be included in future manuscripts. Exploratory analyses not necessarily identified in this SAP may be performed to support planned analyses. Any post-hoc or unplanned analyses not specified in this SAP will be clearly identified as such in the Clinical Study Report (CSR) and manuscripts for publication.

The SAP is a supplement to the study protocol, which should be referred to for additional details on study design, study conduct, and other operational aspects of the study.

The structure and content of the SAP provides sufficient detail to meet the requirements identified by the Food and Drug Administration and International Conference on Harmonisation (ICH) E9: Guidance on Statistical Principles in Clinical Trials. All work planned and described in the SAP will follow internationally accepted guidelines published by the American Statistical Association. The following documents were also considered in preparation for writing this SAP:

- Clinical Research Protocol CAP-1002-DMD-01, Amendment 3.0, July 18, 2016
- ICH E3 Guideline: Structure and Content of Clinical Study Reports
- ICH E6 Guideline on Good Clinical Practice
- ICH E8 General Considerations for Clinical Trials

## **1. INTRODUCTION**

Duchenne muscular dystrophy (DMD) is a pediatric-onset, genetic disease in which patients lack dystrophin, a protein critical for stabilizing muscle cell membranes. Affecting 1 in 3,500-5,500 male births, DMD accounts for 80% of all cases of muscular dystrophy. Patients experience progressive skeletal muscle weakness and loss of ambulation by age 15, eventual respiratory and cardiac failure, and an abbreviated lifespan. With the use of corticosteroids and noninvasive ventilation to treat respiratory muscle disease, heart failure has emerged as the main cause of death in DMD patients. Approved therapies for the underlying disease currently are limited to eteplirsen, an exon 51 skipping agent in dystrophin pre-mRNA to enable the synthesis of a shortened and functional form of dystrophin protein. Allogeneic cardiosphere-derived cells (CAP-1002) are an investigational product consisting of allogeneic cardiosphere-derived cells, known to secrete numerous bioactive elements upon delivery, which is thought to lead to global cardiovascular benefits. The HOPE-Duchenne Phase 2 trial will be the first investigation of CAP-1002 in male subjects with cardiomyopathy secondary to DMD and the first trial of the product not conducted exclusively in adults. The delivery approach will be multivessel intracoronary infusion to distribute the cells throughout the myocardium.

## **2. STUDY OBJECTIVES, TREATMENTS, AND ENDPOINTS**

### **2.1 Objectives**

The primary objective of HOPE is to evaluate the safety and tolerability of CAP-1002 administered by multi-vessel intracoronary infusion in subjects with cardiomyopathy secondary to DMD.

The secondary objective of HOPE is to explore the efficacy of CAP-1002 administered by multi-vessel intracoronary infusion in subjects with cardiomyopathy secondary to DMD.

### **2.2 Treatment Group Comparisons**

Two treatment groups will be compared in the study:

- CAP-1002 (single administration of 75 million (M) cells split into a triple vessel infusion of 25 M cells each)
- Usual Care

### **2.3 Study Assessments**

#### **2.3.1 Safety Assessments**

Safety will be assessed at 6 and 12 months post infusion or reference date unless otherwise noted. For usual care subjects, the reference time point will be randomization date + 7 days at 9:00 a.m. (subject's local time).

1) Adjudicated clinical events:

- a) The following events occurring during or post infusion or reference time point:

- For subjects who receive CAP-1002 only, new TIMI flow 0-2 or TIMI myocardial perfusion grade (TMPG) 0-2, noted immediately following intracoronary infusion of investigational product (IP) and persisting > 3 min after IP infusion, despite intracoronary vasodilator administration.
- Within 72 hours of intracoronary infusion or reference time point, sudden unexpected death defined as occurring within 1 hour of symptom onset, or unwitnessed death in a person previously observed to be well within the preceding 24 hours without an identified cause.
- Major adverse cardiac events (MACE) within 72 hours of intracoronary infusion or reference time point, including death, non-fatal myocardial infarction and hospitalization for cardiovascular event (including heart failure hospitalizations). Evidence of myocardial injury will be assessed by a rule out myocardial infarction (MI) cardiac enzyme protocol following IP administration. Among subjects who receive CAP-1002, troponin and creatine phosphokinase MB isoenzyme (CK-MB) will be obtained every 8 hours for 20-24 hours after IP infusion.

b) Sudden unexpected death defined as occurring within one hour of symptom onset, or unwitnessed death in a person previously observed to be well within the preceding 24 hours without an identified cause.

c) MACE, including death, non-fatal myocardial infarction, hospitalization for cardiovascular event (including heart failure hospitalizations), emergency room treatment for heart failure, left ventricular assist device or heart transplant.

d) Any hospitalization due to a cardiovascular cause.

e) Any inter-current cardiovascular illness which prolongs hospitalization.

f) Development of, or an increase in the frequency of, ventricular tachycardia (VT) with duration of 30 seconds or longer ascertained by protocol mandated continuous cardiac monitoring via Holter Monitor or ZIO® Patch.

g) Development of increased anti human leukocyte antigen (HLA) antibody levels with development of sensitization to HLA antigens specific to the CAP-1002 CDC donor. Elevation of donor-specific antibodies (DSA) is defined as mean fluorescence intensity (MFI) above a threshold of 5000; a threshold of 1000 MFI will also be used to evaluate elevation of DSA. See [Section 9.1](#) for details related to comparison between CAP-1002 and usual care subjects.

2) Adverse events (AEs)

3) Concomitant medications

4) Change from baseline in laboratory evaluations

5) Peak elevation in troponin and CK-MB levels following IP infusion or on reference date

- 6) Changes from baseline in vital signs, weight, and body mass index (BMI)
- 7) Changes from baseline on general and cardiac physical examinations
- 8) Changes from baseline in electrocardiogram (ECG), both 12-lead ECG and continuous cardiac monitoring

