## 1 INTRODUCTION

Duchenne Muscular Dystrophy (DMD) is a pediatric onset, genetic disease in which patients lack dystrophin, a protein critical for stabilizing muscle cell membranes. Affecting 1 in 3,500-5,500 male births, DMD accounts for 80% of all cases of muscular dystrophy. Patients experience progressive skeletal muscle weakness and loss of ambulation by age 15, eventual respiratory and cardiac failure, and an abbreviated lifespan averaging only three decades (Bushby, Finkel et al. 2010a, Bushby, Finkel et al. 2010b). With corticosteroids and non-invasive ventilation, heart failure has emerged as the main cause of death. Yet the overwhelming majority of clinical trials in DMD have focused on skeletal rather than cardiac muscle disease. Without any functional dystrophin protein, cardiomyocytes experience a disruption of membrane integrity, leading to an overload of intracellular calcium, leading to cardiomyocyte death. Cell death is accompanied by local inflammation which serves as a source of oxidative stress for the remaining cardiomyocytes (Shirokova and Niggli 2013). These foci of cell death are often experienced by patients as microinfarcts, and accompanied by chest pain and the release of cardiac enzymes, clinical hallmarks of MI. This amplifying process triggers progressive scar tissue deposition and leads eventually to heart failure. Improvements in the treatment of respiratory muscle disease have elevated the inevitable cardiomyopathy to the leading cause of death in DMD patients (Spurney 2011, Passamano, Taglia et al. 2012).

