**Table 2. Local Laboratory Testing, Day 0 and Day 1 (CAP-1002 Arm Only)**

Pre-Infusion	Post-Infusion
Troponin I	Troponin I ( serial collection )
CK-MB	CK-MB ( serial collection )
Serum Chemistry*	Serum Chemistry*
Hematology*	Hematology*
Urinalysis*	Urinalysis*
PTT & INR (if taking warfarin)	

\*See Appendix 2 for details

Serum for the donor specific antibody (DSA) monitoring, HLA typing and blood for the ELISpot assay will be collected and processed at each site and then shipped to a central core laboratory for analysis within 24 hours of obtaining the specimens (See Laboratory Manual for shipping instructions). Subjects will be monitored for the development of a cellular immune response using the ELISpot (enzyme-linked immunosorbent spot) assay. The ELISpot assay will be performed at screening and at the Week 6 study visit.

Serum for research purposes (biomarkers) will be collected and processed at each site then shipped to a central core lab that will then ship to Capricor for final storage and analysis (if subject has provided consent).

For subjects who provide consent and/or assent, serum for clinical research into biomarkers will be collected at every scheduled visit (excluding infusion) and sent to the Sponsor, or designee, for storage and/or analysis (including and future analysis). Per the Code of Federal Regulations (21 CFR 320.38), serum samples collected from study subjects will be maintained in storage for at least five (5) years following the date on which the IND application or supplemental application is approved. If such application or supplemental application is not approved, serum samples will be maintained in storage for at least 5 years following the date of completion of the clinical research study.

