### 7.3 Data Analysis

- The anchor date used for summaries and analyses will depend on the analysis population, as follows:
  - ITT population: randomization date
  - mITT population: IP administration or reference date

- Safety population: IP administration or reference date
- Per protocol population: IP administration or reference date
- Categorical variables will be summarized as frequencies and percentages in each category. Percentages will be reported to one decimal place. Unless otherwise noted in Sections 8-10, categorical variables will be analyzed using chi square tests of association or, if any contingency table cell has less than 5 subjects, Fisher's exact test.
- Continuous variables will be summarized by numbers of subjects, means, standard deviations, medians, and ranges. The number of decimal places for minimums and maximums will be the same as the original data. The number of decimal places for means, medians, and interquartile ranges will be the same as the original data plus one. The number of decimal places for measures of variance will be the same as the original data plus two. Unless otherwise noted in Sections 8-10, continuous variables will be analyzed using t-tests or, if appropriate, analysis of covariance with baseline as a covariate. Non-parametric tests and data transformations will be considered for variables with distributions that violate parametric assumptions.
- Data with qualifiers (e.g., “<”) will be listed with but summarized without the qualifier.
- P-values will be presented to two decimal places if  $> 0.01$ , to three places if  $< 0.01$  but  $> 0.001$ , and to four places if  $< 0.001$  but  $> 0.0001$ . P-values  $< 0.0001$  will be presented as “ $< 0.0001$ .”
- Statistical tests will be two-sided and tested at the 0.05 significance level unless otherwise noted in Sections 8-10.
- It is understood that statistical non-significance is not an indicator of equivalence.

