### 9.1 Adjudicated Clinical Events

Clinical events, described in [Section 2.3.1](#), will be adjudicated by an independent Clinical Events Committee (CEC) (see [Section 12](#)). Each event will be summarized as frequency and percentage of subjects who experienced the event. In addition, a composite event will be defined as new TIMI flow 0-2 or TMPG 0-2 (CAP-1002 subjects only), sudden death, or MACE during or following IP administration or reference time point. For the composite and its components, summaries will include exact 90% confidence intervals (CIs) for both treatment groups. For peri-procedural events other than TIMI flow 0-2 or TMPG 0-2, summaries will include a 90% CI for the difference in proportions between treatment groups, and the one-sided p-value from an exact binomial test of the difference between treatment groups. For all other clinical events, assessed over the length of the trial, event rates per 100 subject-years will be calculated and, if applicable, treatment groups will be compared using negative binomial regression with an offset for days of follow-up (log transformed). If the dispersion parameter is not significantly different from zero, Poisson regression will be used instead.

For the analysis of development of increased HLA antibodies to HLA antigens specific to the CAP-1002 donor, incidence of increased HLA antibody levels specific to the donor will be summarized and analyzed; for usual care subjects, a random donor will be selected from those that were matched to the subject during screening. Elevated levels of donor specific antibodies will also be summarized and analyzed by time point for all nominal time points at which samples were collected for DSA testing. Analyses will be performed using both 1000 and 5000 MFI as the threshold for defining increased HLA antibodies.

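### The 72-hour MACE comparison between arms includes MI, which is sought by serial enzymes only in CAP-1002 subjects, so for that component treatment effect and ascertainment are confounded

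*SAP*

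**What the plan says.** SAP 2.3.1 defines MACE within 72 hours of infusion, or of the usual-care reference time, as death, non-fatal MI or cardiovascular hospitalization. The same item describes how myocardial injury is looked for: "Among subjects who receive CAP-1002, troponin and creatine phosphokinase MB isoenzyme (CK-MB) will be obtained every 8 hours", over the 20-24 hours that follow infusion. Protocol 6.5.2 and Table 2 restrict Day 0 and Day 1 laboratory tests to the CAP-1002 arm.

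Protocol Appendix 1 gives usual-care subjects no Day 0 visit and no actual Day 1 visit. Their scheduled troponin and CK-MB draws are at screening, Week 2, Month 6, Month 12 and early termination. Inside the 72-hour window they have home rhythm monitoring from Day 1 and a Day 3 telephone call, which Protocol 7.3 allows as late as Day 6.

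SAP 9.1 sets the analysis: "For peri-procedural events other than TIMI flow 0-2 or TMPG 0-2, summaries will include a 90% CI for the difference in proportions", together with "the one-sided p-value from an exact binomial test of the difference between treatment groups". 72-hour MACE falls under that rule. MI is not exempted, and no analysis without enzyme-only MI is planned.

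SAP 2.3.1 item 5 refers to peak troponin and CK-MB after infusion or on the reference date. The protocol schedule collects no usual-care sample on that date.

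**The concern.** Safety is the primary objective, and this is one of the few between-arm comparisons the SAP specifies for it. An MI that shows only as an enzyme rise can be found in an infused subject but not in a usual-care subject, because no blood is drawn. The Protocol Introduction gives reason to expect some background: foci of cell death in DMD are "often experienced by patients as microinfarcts, and accompanied by chest pain and the release of cardiac enzymes". Any such background is looked for systematically in one arm.

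Two errors are possible. Unequal detection could produce an apparent excess in CAP-1002, or a real procedural excess could be dismissed as an artefact of detection. The data as planned cannot tell these apart.

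**Working it through.** **Inputs from the documents.** About 12 subjects per arm, at most 30 in total (SAP 3 and 4); a one-sided exact test (SAP 9.1); tests "tested at the 0.05 significance level unless otherwise noted in Sections 8-10" (SAP 7.3). The plan gives no expected MACE or MI rate, no power and no p-value for this endpoint, so there is no figure of its own to reproduce.

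**Assumptions.** Let q be the true 72-hour probability of an MI detectable only by serial enzymes, equal in both arms (no treatment effect). Let d be the fraction of these detected in usual care. No other MACE occurs. The one-sided level is 0.05, which matches the 90% CI, in the direction of a CAP-1002 excess. The SAP does not name the exact test, so both Fisher (conditional) and Boschloo (unconditional) are shown.

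**Bias in the estimate.** Expected difference = q − dq = q(1 − d). At q = 10%, d = 0 this is +10 percentage points against CAP-1002, or 12 × 0.10 = 1.2 expected events against none. At q = 20%, d = 0.5 it is again +10 points. The bias does not depend on which test is used.

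**Events needed for p < 0.05, with none in usual care (12 per arm).**
- 3 v 0: Fisher p = 0.109; Boschloo p = 0.048.
- 4 v 0: Fisher p = C(12,4)/C(24,4) = 495/10,626 = 0.047; Boschloo p = 0.018.

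With d = 0, false significance is therefore P(Bin(12, q) ≥ 4) for Fisher and P(Bin(12, q) ≥ 3) for Boschloo:

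| Assumed q | Fisher | Boschloo |
|---|---|---|
| 5% | 0.2% | 2.0% |
| 10% | 2.6% | 11.1% |
| 20% | 20.5% | 44.2% |
| 30% | 50.7% | 74.7% |

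The probability passes 5% at q of about 12% (Fisher) or 7% (Boschloo).

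**Variations.** With half of the events detected in usual care (d = 0.5) and q = 20%, the figures are 6.6% (Fisher) and 15.3% (Boschloo). With 15 per arm and d = 0, Fisher gives 5.6% at q = 10% and 35.2% at q = 20%.

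**Check with equal ascertainment (d = 1, 12 per arm).** For q from 5% to 40%, rejection is 0.1% to 3.0% (Fisher) and 1.1% to 4.7% (Boschloo), within the nominal 5%. The excess above that comes from unequal detection.

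**The case against.** The strongest points on the other side are these.

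- **Only one component is affected.** Death and hospitalization are followed in both arms, and under SAP 12 the CEC adjudicates events within 24 hours of infusion or the reference time in both. This stands. A reader might infer that the test measures only surveillance; the documents do not support that. A CAP-1002 excess could be real procedural injury, and Protocol 7.13.5 lists limited troponin elevation as expected after infusion. But neither the CEC nor the Day 3 call can recover enzymes that were never drawn.
- **TIMI is not a precedent on ascertainment.** A reader might infer that the SAP leaves TIMI/TMPG out of the comparison because of unequal detection. The SAP gives no reason, and Protocol 3.1 treats such findings as relevant only to the active arm. MI can occur in either arm. TIMI shows only that reporting for one arm is already accepted in this plan.
- **The background is unquantified.** The Introduction describes events with chest pain, some of which could come to light in usual care, and gives no frequency for silent ones. At q = 5% or 10% the Fisher figure is below 5%. Whether an enzyme rise alone would be adjudicated as MI depends on consensus definitions outside these documents. All this stands, and the probabilities are conditional on it.
- **The bias is conservative and no decision rule hangs on the p-value.** Both are true, and they limit the severity. Neither makes the estimate interpretable: in a safety comparison, a false signal and a discounted true one are both harmful.
- **Some description is already planned.** SAP 9.1 gives exact 90% CIs per arm, and SAP Appendix B lists adverse-event tables for subjects with peri-procedural troponin elevations and a CAP-1002-only post-infusion enzyme plot. These help interpretation but leave the between-arm comparison unchanged.

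**Conclusion.** The point holds for the non-fatal MI component of 72-hour MACE. As planned, the between-arm difference for that component confounds treatment effect with ascertainment and is biased against CAP-1002 by q(1 − d). That follows from the schedule and SAP 9.1 alone.

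The size is not known. The range from 0.2% to 50.7% for q from 5% to 30% rests on assumed rates, no usual-care detection, 12 per arm, an assumed Fisher test, and enzyme-only events being adjudicated as MI. Boschloo's test would give higher figures at 12 per arm.

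A reader might also take the composite of TIMI/TMPG, sudden death and MACE to be tested between arms. SAP 9.1 clearly plans only per-arm intervals for it, so this point does not extend to a test of the composite.

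**What to change.** 1. Have the CEC flag each MI within 72 hours that was identified only by the protocol-mandated enzyme draws.
2. Report flagged MIs for CAP-1002 only, with an exact 90% CI.
3. Give the between-arm 90% CI and one-sided p-value for 72-hour MACE on death, clinically presenting MI and cardiovascular hospitalization. Show the all-MI version beside it, so that no event is hidden.
4. Footnote that surveillance still differs: infused subjects have 20-24 hours of inpatient telemetry and usual care has none, so clinically presenting MI is not sought equally either.
5. Name the exact test, its direction and its level.
6. Reconcile SAP 2.3.1 item 5 with the protocol schedule on usual-care enzymes at the reference date.
7. Do not add a between-arm test of the composite.

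The cost is SAP wording, one CEC flag and a second version of 72-hour MACE to explain. No extra visit or blood draw is needed. This is a cheap improvement: it removes enzyme-only detection from the comparison but does not make surveillance equal.

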### **2.3.2 Exploratory Efficacy Endpoints**

The following exploratory efficacy endpoints will be assessed at 6 and 12 months post infusion or reference date:

- 1) Change from baseline in cardiac structural parameters measured by magnetic resonance imaging (MRI), including:
  - LV late gadolinium enhancement (LGE) expressed as a percent of LV mass
  - LV LGE expressed in grams
  - LV viable mass expressed in grams
  - Number of LV segments with LGE
  - LV circumferential strain
  - Left ventricular ejection fraction (LVEF)
  - LV end diastolic volume (LVEDV) and LV end systolic volume (LVESV)
  - LV stroke volume
  - Regional LV function assessment

LGE and circumferential strain will be assessed both overall as well as by individual segment and by groups of segments (e.g., infusion location, septum, base, LV free wall).

- 2) Rate of change since baseline compared to rate of change from historical MRI to baseline in LV LGE (overall and by individual segment and groups of segments)
  - expressed as a percent of LV mass
  - expressed in grams
- 3) Change from baseline in functional parameters:
  - Performance of Upper Limb (PUL) scale
  - Spirometry
  - 6-minute walk test (6MWT) in ambulatory patients
- 4) Change from baseline quality of life (QoL) parameters:
  - Pediatric Quality of Life Inventory (PedsQL), including the cardiac module
  - Pediatric Outcomes Data Collection Instrument (PODCI) Adolescent Questionnaire
- 5) Change from baseline in biomarkers:
  - Osteopontin
  - ST2
  - Interleukin 10 (IL-10)
  - Galectin-3

[figure not shown]
